\$20 for completing the baseline, \$5/week for diaries with 5/7 days completed (or TLFB interview completed) plus a \$30 bonus for completing all 5 weeks, \$50 for final survey, and \$50 for qualitative interview (potential total: \$175). **Fidelity.** The research team will review all call recordings, code for treatment fidelity and collaborate with QC supervisors to review standard call quality metrics. Feedback will be provided to coaches. **Feedback from QCs.** Feedback from QCs on challenges with the EEC and recommendations for improvement, which will be used to refine the EEC prior to Phase 2. **Measures.** (Table 2.) Baseline. Standard QL registration includes demographic and tobacco use questions. Prior to randomization, participants will complete additional measures on ENDS and cessation medication use, knowledge and beliefs (questions from the empirical literature or developed to assess key misconceptions targeted by EEC education), and brief assessments of psychosocial functioning (depression, stress, anxiety). Treatment Adherence/ Engagement. Call completion, call minutes, and NRT sent from the QL are standardly captured data. Daily diaries. Participants will complete brief diary assessments on their use of ENDS, cessation medications, and traditional tobacco products, as well as cravings and an open-ended question on quit challenges (1-5 minutes to complete; procedures will be refined to facilitate completion during Phase 1 Pilot). Diaries can be completed (1) online via emailed mobile-optimized survey links or (2) via paper measures that will be returned by mail weekly. RAs will provide orientation to diary completion, and will closely track online completion and mailed surveys to provide reminders. Nonresponders (<5/7 days completed) will be contacted by a RA to complete a brief TLFB interview by phone. Multimodal Outcome Survey. The outcome survey will include measures used at Baseline (see Table 2) plus: (1) Program Satisfaction and Acceptability: assessed via a 10 Likert-rated item questionnaire (e.g., Would you recommend this to a friend?) and, for the EEC group only, several open-ended questions (e.g., what would you change about this program?) developed based on the methodology outlined by Dumas and Redish; (2) Treatment Adherence: questions will assess use of EEC educational materials (EEC only) and use of print materials (both groups); (3) SDM: the 3-item Collaborate scale will assess coach effort in helping participants understand quitting options, eliciting participant preferences, and integrating preferences in QP decision making, and (4) adverse events during treatment and specifically during ENDS or cessation medication use. Surveys will be emailed with a link for online completion, followed by multiple attempts to complete by phone, and finally a truncated paper survey will be mailed. Qualitative Interviews. After program completion, trained interviewers will conduct an interview to assess: (1) ENDS, NRT, and nicotine beliefs (relative harm, safety, long-term use), (2) quit strategies used and how and why ENDS were used during the program, (3) reactions to SDM model for QP development, and confidence in and adherence to QP, (4) use of and reactions to EEC print materials, (5) reactions to coaching calls and education from QCs, (6) why/why not callers would recommend the program and recommendations for improvement, and (7) diary completion experiences. Findings will be used to augment other data to determine readiness for Phase 2, as well as to refine the treatment and measures. **Criteria for Proceeding to Phase 2.** 8/10 participants would recommend the EEC to other ENDS users. 7/10 report improved knowledge about ENDS and NRT. 7/10 articulate QPs that include adaptive, but not maladaptive strategies. Iterative changes will be made to the EEC; if benchmarks are not met, we will recruit for Phase 1 until the EEC is ready.

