### **2.3c Phase 2: Randomized pilot to test feasibility and acceptability, and explore preliminary efficacy.**

**Design.** Pilot study with 100 ENDS and cigarette dual users randomized (1:1) to EEC intervention or QL TAU. Phase 2 will use the same EEC intervention and procedures described and refined in Phase 1 with several

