exceptions described below. **Procedures.** *Recruitment, Study Offer, and Consent.* Participants who meet eligibility criteria based on standard registration questions will be asked if they would like to participate. Interested dual users will then be asked if they are willing and able to complete short daily questionnaires. Those who respond yes will be called back by a QC to complete consent, baseline measures, and be randomized to TAU or EEC. Randomization will be stratified by gender to ensure equal representation of males and females in each group. Participants will then immediately receive their first coaching call. *Inclusion Criteria.* Same as Phase 1. On average, 140 OKHL callers report ENDS use each month. Based on previously conducted studies, we estimate 40% (56) will meet other eligibility criteria, from which we expect to be able to recruit 80% (44) per month, allowing us to easily reach our  $N=100$  goal over 6 months. *EEC Intervention Protocol.* The EEC intervention will be developed and refined as described in Phase 1 and will follow the call schedule in Table 1. *QL TAU (Control).* The QL program (described in Table 1) has been proven effective and cost-effective in numerous clinical trials and evaluations for the general population of smokers. AWI's general approach for addressing ENDS during coaching calls was described above; however, our qualitative work suggested ENDS are often not discussed or only discussed briefly on calls. **Fidelity.** The research team will review call recordings and complete fidelity coding for 20% of EEC and TAU calls. Feedback will be provided to coaches weekly. Other fidelity domains will be reviewed and rated per procedures outlined by Borrelli and colleagues. **Measures.** All measures and compensation are as described in Phase 1 with three exceptions: (1) additional measures or measure changes needed based on Phase 1 work, (2) Outcomes Survey will be completed at 3-months post-registration in Phase 2 (in Phase 1, outcomes will be assessed at end of treatment), and (3) Qualitative interviews will be completed with 10 EEC participants total. In line with published recommendations, we are not including biochemical abstinence verification due to no face-to-face contact and no expectation for systematic reporting bias across groups. Moreover, the primary goal of the EEC is smoking cessation at 3 months. Participants may or may not be using ENDS at that time. ENDS use can result in salivary cotinine levels similar to cigarette smoking and that exceed standard biomarker thresholds, which limits utility for assessing smoking abstinence in this study. **Strategies to Minimize Attrition.** Our team has obtained outcome survey response rates of 80% using multiple modalities (phone, email, mail), incentives, and alternative contacts provided at baseline. [name] team has achieved diary completion rates of 59% in weeks 1 and 2 of an adaptive intervention study including ENDS devices; we aim to improve these rates with additional incentives, monitoring and reminder protocols. We will use participant retention and education strategies addressing research participation and engagement in consent materials. Call completion will be monitored and improvements made (e.g., increasing attempts) if needed.

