
**2.4d Statistical Analysis.** Participant baseline characteristics and program engagement will be summarized using proportions (with 95% confidence intervals (CIs)) and means (with SEs). We will use regression (and non-parametric rank sum tests) to examine primary hypotheses that, at 3-months, EEC participants will (1) have completed as many or more calls, (2) have satisfaction rates at least as high and rate QP development experiences more positively, and (3) report more accurate beliefs about ENDS, smoking, and quit medications, compared to TAU. Secondary outcome analyses will examine rates of 7-day point prevalence smoking abstinence and of ENDS and cigarette dual use. The control and EEC groups will be compared using logistic regression for binary outcomes or ANCOVA for continuous outcomes, while controlling for relevant baseline data (caller characteristics, nicotine dependence, smoking history). Diary data will be reviewed to categorize frequency and characteristics of ENDS, cessation medication, and cigarette use. We will explore correlates of outcomes based on product use reported on diaries to examine potential mechanisms that lead to smoking cessation or continued dual use of cigarettes and ENDS. Finally, we will explore potential group differences or moderators of treatment engagement and outcomes (e.g., gender, age, race/ethnicity, reasons for ENDS use).

We will address missing values multiple ways: 1) analyzing existing data (responders), 2) assuming worst case (smoking) for missing, 3) using multiple imputation, and 4) conducting sensitivity analyses with different non-responder relapse probabilities to determine how extreme values would need to be to invalidate results. For all aims, preliminary analyses will include summary statistics, cross tabulations of outcomes and baseline variables by group, and correlations. Standard regression diagnostics will be performed.

**Sample Size/Power.** Assuming 30% loss-to-follow-up, we will have 3-month outcomes for 35 per group, which aligns with Pilot/Stage I study recommendations. While this feasibility study is not powered to identify significant differences at the 5% alpha level, examination of CIs can identify outcomes or moderators worth investigation in a larger trial and inform treatment refinement, while avoiding over interpretation of effects.

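### Do the two not-worse hypotheses (calls completed, satisfaction) need a stated rule for reading a non-significant difference?

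*SAP*

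**What the plan says.** SAP 2.4d (Statistical Analysis) gives one method for all the primary hypotheses: "We will use regression (and non-parametric rank sum tests) to examine primary hypotheses". Hypothesis 1, on the number of coaching calls completed, and the start of hypothesis 2 read: "at 3-months, EEC participants will (1) have completed as many or more calls, (2) have satisfaction rates at least as high". Hypothesis 2 in full is that EEC participants will "have satisfaction rates at least as high and rate QP development experiences more positively". The calls hypothesis and the satisfaction half of hypothesis 2 are not-worse claims. The quit-plan half of hypothesis 2, and hypothesis 3 on accuracy of beliefs, are superiority claims and are not in question here.

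Three other statements in 2.4d bear on how results will be read:

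- Its opening sentence plans summaries of program engagement as proportions with 95% confidence intervals and means with standard errors. The measures table in the SAP classes call completion as engagement data.
- For all aims it plans cross-tabulations of outcomes by group.
- The Sample Size/Power paragraph says: "While this feasibility study is not powered to identify significant differences at the 5% alpha level", and continues that "examination of CIs can identify outcomes or moderators worth investigation in a larger trial and inform treatment refinement, while avoiding over interpretation of effects".

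SAP 2.3c titles Phase 2 as a "Randomized pilot to test feasibility and acceptability, and explore preliminary efficacy". The only numerical progression benchmarks, such as "8/10 participants would recommend the EEC to other ENDS users", are single-arm and govern the move from Phase 1 to Phase 2. The satisfaction measure (SAP 2.3b, Measures) is a set of ten Likert-rated items in the outcome survey. The text does not say how a satisfaction rate is formed from them.

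**The concern.** A regression or rank-sum p-value tests whether the arms differ. A significant result in favour of EEC would support a not-worse claim, and one in favour of TAU would count against it. A non-significant result does neither. In a small trial it is also the most probable result over a wide range of true effects, including ones where EEC is worse.

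For a superiority hypothesis, low power makes a favourable claim harder to reach. For a not-worse hypothesis read through non-significance, low power makes it easier. The SAP's admission of low power is therefore not, taken alone, a safeguard for these two outcomes.

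If a report took non-significance as confirmation, the pilot could conclude that EEC kept callers engaged and satisfied when the data could not exclude a real deficit. Calls and satisfaction are the main engagement and acceptability evidence, and the SAP overview (2.3) says the results will help decide whether a full trial is warranted.

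**Working it through.** **Inputs from the documents.** 100 participants randomised 1:1 (SAP 2.3c). The protocol's Phase 2 target is 50 per group who take at least one call. Loss to follow-up is 30% (SAP 2.4d). Response reached 80% in the team's earlier surveys (SAP 2.3c). Call completion is captured routinely, so 50 per group is usable for calls. Satisfaction comes from the survey, so 35 per group applies (40 at 80% response).

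**The plan's own figure.** 50 × (1 − 0.30) = 35 per group, as stated. The SAP gives no SD, rate, effect size or margin. Those used below are assumptions.

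**Chance of a non-significant result when EEC is truly worse** (normal approximation, two-sided 5%): P = Φ(1.96 − δ/SE) − Φ(−1.96 − δ/SE), where δ is the true deficit.

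*Calls, 50 per group, δ = 0.5.* SE = SD × √(2/50) = 0.2 × SD.

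| SD | SE | 95% CI half-width | P(non-significant) |
|---|---|---|---|
| 1.0 | 0.20 | 0.39 | 29% |
| 1.5 | 0.30 | 0.59 | 62% |
| 2.0 | 0.40 | 0.78 | 76% |

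SD 2.0 is the ceiling for values from 1 to 5, since (5 − 1)/2 = 2.0. It requires a mean of 3.0, so two arms that differ by 0.5 cannot both have it, and the last row is a bound. A simulated rank-sum test, with TAU calls spread evenly over 1 to 5 and an EEC mean of 2.5, was non-significant in 57% of trials.

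*Satisfaction as a proportion, δ = 0.10.* SE = √[(p₁(1 − p₁) + p₂(1 − p₂))/n]. For TAU 80% and EEC 70% with n = 35: √[(0.16 + 0.21)/35] = 0.1028.

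| TAU rate | P, 35 per group | P, 40 per group |
|---|---|---|
| 90% | 78% | 76% |
| 85% | 82% | 80% |
| 80% | 84% | 82% |
| 75% | 85% | 83% |

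Exact enumeration of the logistic Wald test at 35 per group gives 84% to 86%.

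*Satisfaction as a score, δ = 0.4 SD.* SE = √(2/35) = 0.239 SD, half-width 0.47 SD, P = 61%. At 40 per group the half-width is 0.44 SD and P = 57%.

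So the statistical premise is right: non-significance says little about either claim.

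**What the planned interval would show.** Suppose both arms are observed at 80% with 35 per group. The half-width is 1.96 × √(2 × 0.16/35) = 0.187, so the 95% CI runs from about −19 to +19 points. Suppose instead EEC is observed at 70%. The half-width is 1.96 × 0.1028 = 0.20, giving about −30 to +10 points. Both tests are non-significant. In both cases the interval shows that a deficit of 10 points is not excluded, and an analyst who examines it, as 2.4d intends, has no basis for claiming that EEC is at least as good.

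**What a formal rule would buy.** With truly equal arms and a 95% CI, a 0.5-call margin at SD 1.5 would be met in Φ(0.5/0.30 − 1.96) = 38% of trials. A 15-point satisfaction margin at 85% would be met in 42% (35 per group) or 47% (40 per group). At 80% power and one-sided 2.5%, satisfaction at 80% in both arms would need 252, 112 or 63 per arm for margins of 10, 15 or 20 points. A pilot with 35 per group cannot deliver that, and the SAP does not ask it to.

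**The case for a change.** The strongest case for a change is that the SAP's cautionary sentence has a different job. It uses confidence intervals to pick outcomes and moderators for a larger trial, and its warning is most naturally read as being about claiming effects too readily. The risk here is the reverse, an absent difference read as equivalence, and nothing in the text names that risk. The two outcomes are primary hypotheses, and one sentence would settle the matter at almost no cost.

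Part of this stands. The SAP does not say how a non-significant result on calls or satisfaction will be read, and a sentence saying that it is not evidence of equality would do no harm. The way in which ten Likert items become a satisfaction rate is also not visible. It may be set out in the study measures attachment that the protocol cites, which is not among the documents, so this cannot be called an omission.

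The case does not show that the plan as written leads to the error. The SAP says regression will be used to examine the hypotheses. It sets no decision by p-value and nowhere treats non-significance as support. A regression with a group term returns the estimated difference with its interval, or an odds ratio if satisfaction is dichotomised. The misreading is a conjecture about later reporting, and it would go against the SAP's own statements on power and intervals. The assumed deficits of 0.5 calls, 10 points and 0.4 SD are also illustrative, since no document calls them important, and the planned baseline adjustment could narrow the intervals by an unknown amount.

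**Conclusion.** No change to the plan is needed. The logical point is correct and its size is real: under the assumed rates and SDs, a true 10-point satisfaction deficit would be non-significant in roughly 76% to 86% of trials across the sample sizes and tests checked, and a true 0.5-call deficit in 29% to 76%, depending mainly on the SD. The harm, however, needs a reading that the SAP neither states nor invites. The same section disclaims power, relies on intervals, cautions against over-interpretation and already summarises engagement with measures of precision. No stated Phase 2 decision rule uses either outcome.

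What is left is an unstated reading convention, which an analyst following 2.4d would supply by reporting the EEC minus TAU difference with its interval, and a scoring detail that may sit in an attachment. A formal margin would add little, because with equal arms the margins examined for calls and 85% satisfaction would be met in only 38% to 47% of trials. This conclusion rests on the results being reported as the SAP describes, as unpowered pilot estimates with confidence intervals.

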### **Recruitment:**

- Participants who call into the Oklahoma Tobacco Helpline (OKHL) will be offered the initial study invitation (*see study scripts*) if they meet the following eligibility criteria:
  - Eligibility Criteria:
    - Requested Coaching Services
    - Reports using E-Cigarettes in the last 30 days
    - English Speaking
    - 18+ years old
    - Not Pregnant
    - Not planning pregnancy in next 3 months
    - Currently using cigarettes
    - Enrolled in 5 Call OKHL program
    - Willing to quit cigarettes in the next 30 days
    - TCPA consented (consents to outbound telephone calls)
    - Not enrolled via Proxy
    - Did not report a diagnosis of Schizophrenia
    - Not previously screened for study
- The OKHL uses a computerized participant record system. Application development work will be completed to display the study offer if an OKHL enrollee meets the above criteria. The study offer will be completed by a registration agent prior to finishing a participant's enrollment into the OKHL.
  - Participants who are not interested in the study will continue to be enrolled in the standard OKHL services.
- Participants who accept the study offer will be asked additional screening questions (*see Study scripts*) that will further determine eligibility into the study.
  - Participants who did not meet additional screening questions will be deemed ineligible for the study and continue with standard OKHL services.
- Those who are deemed eligible will be read the Final Study Invitation (*see Study scripts*) and their response will be collected.
  - Those who decline the study invitation will not continue with the study and instead be enrolled in standard OKHL services.
- Those who accept the study invitation will be transferred to a study-trained coach who will complete study consent, baseline and randomization to one of the two treatment groups.
  - Participants will be warm transferred to a study coach if one is available. If not, participants will be informed that a study coach will call them back to complete study enrollment.

- If participants do not connect with a study coach to complete study enrollment after at least 5 attempts have been made, they will no longer be eligible to continue in the study and will continue with standard OKHL services.

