**Regardless of whether ENDS help people quit smoking, treatment providers need to know the best way to address ENDS during smoking cessation treatment among current dual users of cigarettes and ENDS.** State funded QLs in the United States provide free, evidence-based, cost-effective tobacco cessation treatment, including phone counseling and NRT. Over 10% of QL callers report current ENDS use at registration, translating to 40,000 dual users entering treatment each year. Alere Wellbeing, Inc. (AWI), the provider of QL services in the proposed study, has a general approach to addressing ENDS: (1) the QL's primary goal is to help cigarette and traditional tobacco users quit, but it will also help with quitting ENDS, (2) Quit Coaches (QCs) are trained to educate that ENDS are not regulated by the FDA as a cessation aid, their long-term safety is unknown, and they are not empirically supported cessation aids, and (3) to not promote ENDS for cessation, but also not to discourage smokers switching to ENDS to quit. We conducted one-month post-registration qualitative interviews with 40 QL callers (i.e., *after* most program calls had been completed) who used ENDS and wanted to quit smoking at registration. ENDS often were not discussed or only briefly discussed on calls and callers perceived a range of ENDS-related messages from QCs (top four: discouraged use, encouraged use, much unknown about, not regulated; see manuscript in Appendix B). The existing protocol and/or deficits in coach confidence in addressing ENDS may lead to variable delivery or limited focus on ENDS. Expert recommendations for addressing ENDS during smoking cessation include recommending empirically supported medications as the first-line treatment, educating about the importance of completely quitting combustible tobacco and what is known about the safety and efficacy of ENDS for quitting smoking, and, for smokers who have failed first-line treatments or are insistent on using ENDS for quitting, to support their quit attempt. Some recommendations are more extensive, noting the superiority of nicotine-containing ENDS, better nicotine delivery and craving reduction with later generation models, use of ENDS with other pharmacotherapies (i.e., combination therapy), use duration, handling and storing of devices, and other safety precautions. **The best way to operationalize these recommendations and help smokers who use ENDS make decisions about their quit plan (QP) has not been examined in previous research.**

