
**Table 1. Call content: QL TAU and EEC Intervention**

Call Number	QL TAU (control)	Enhanced ENDS Coaching (EEC) Intervention
Addressed in every call	Intervention grounded in social cognitive theory and US PHS clinical guidelines. Assessment of current status and challenges. Modify medications or set new quit date if needed.	All EEC calls will include key QL TAU components PLUS behavioral support and education regarding ENDS use (if currently using). EEC educational booklets will be referenced. Additional call-specific components noted below.
1: Assessment & Planning	Program overview, assessment and planning with focus on setting a quit date, cessation medications, urge management, tobacco proofing and support. Quit Guide mailed.	(1) Assessment of ENDS use and intentions for use, (2) ENDS education, and (3) SDM on use of ENDS and FDA-approved cessation medications in QP. Tailored EEC educational booklet #1 mailed to participant.
2: Pre-quit date	Motivational enhancement, reinforce QP.	Reinforce QP including use of ENDS and/or medications.
3: Quit date	ACE model (avoid, cope, escape), social support, tobacco proofing.	Tailored EEC educational booklet #2 mailed to participant.
4: Quit date follow-up	Relapse prevention (RP), ACE.	If current using ENDS: (1) RP addressing plans for ENDS use, (2) address intentions for long-term use of ENDS.
5: Ongoing	RP, ACE, summarize and wrap up program.	Same additional content as call 4.
NRT provision	Same for both groups. All are eligible for 2-8 weeks of NRT (depending on insurance status) if they medically qualify and/or return a medical override letter from their doctor (see Human Subjects/Risks of NRT for more detail).	
NRT dosing	Typically based on CPD prior to start of dual use, but also utilizes QC judgement guided by an established dosing protocol. Strongly encourages stopping all non-NRT forms of nicotine (including ENDS) on quit date.	Participants will work with coaches using SDM to determine plans for ENDS and NRT use while quitting. NRT dosing will be adjusted if participants plan to continue ENDS use. QCs will assess potential side effects and QP adherence on every call and make needed adjustments to the QP or NRT dosing.

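### Could the 3-month dual-use rate be misread as a cessation result, because people who smoke only cigarettes count as not dual alongside quitters?

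*SAP*

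**What the plan says.** SAP 2.4d names two secondary outcomes in one sentence: "Secondary outcome analyses will examine rates of 7-day point prevalence smoking abstinence and of ENDS and cigarette dual use". Seven days is attached to abstinence; no window is attached to dual use. Binary outcomes are compared by logistic regression. The same section plans cross tabulations of outcomes by group, a review of diary data to categorise ENDS, medication and cigarette use, and four treatments of missing values, one of which counts non-responders as smoking.

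On ENDS in the two arms, the NRT dosing row of SAP Table 1 says of usual quitline treatment (TAU): "Strongly encourages stopping all non-NRT forms of nicotine (including ENDS) on quit date". Of the enhanced ENDS coaching arm (EEC) it says: "Participants will work with coaches using SDM to determine plans for ENDS and NRT use while quitting". SAP 2.1 describes the quitline's general approach more softly, as "to not promote ENDS for cessation, but also not to discourage smokers switching to ENDS to quit", and SAP 2.3c adds that "our qualitative work suggested ENDS are often not discussed or only discussed briefly on calls".

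SAP 2.3c makes smoking cessation at 3 months the primary goal of EEC and says of ENDS: "Participants may or may not be using ENDS at that time". At entry the Protocol (Phase 2, Recruitment) asks for a person who "Reports using E-Cigarettes in the last 30 days".

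**The concern.** At 3 months a participant is in one of four states: both products, cigarettes only, ENDS only, or neither. The dual-use rate isolates the first and merges the other three, so a lower rate can mean that people stopped smoking or that they stopped ENDS and went on smoking. If usual treatment moves more continuing smokers off ENDS than EEC does, EEC would show more dual use with no difference in cessation.

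The abstinence rate repairs this only in part. Cigarettes only equals one minus abstinence minus dual use, provided that both rates share a window and a denominator. Even then, the two rates cannot separate ENDS only from neither. Counting missing people as smoking also leaves their ENDS use unstated.

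The stake is the choice of outcomes for a larger trial. SAP 2.4d will use confidence intervals for that choice, and a dual-use interval could be taken as a cessation signal.

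**Working it through.** **The plan's own figure.** SAP 2.3c randomises 100 at 1:1, and SAP 2.4d assumes 30% loss: (100/2) × (1 − 0.30) = 35 per group, as stated.

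**Inputs.** The documents give no expected outcome rates. All shares and counts below are assumptions.

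**1. Can equal dual use hide unequal cessation?** Take 35 per arm, in the order both / cigarettes only / ENDS only / neither.

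- Arm A, 14/3/12/6: dual use 14/35 = 40.0%; abstinent 18/35 = 51.4%.
- Arm B, 14/14/3/4: dual use 14/35 = 40.0%; abstinent 7/35 = 20.0%.

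Dual use is identical, but the abstinence rate planned beside it separates the arms. On a shared window, cigarettes only follows by subtraction: 100 − 51.4 − 40.0 = 8.6% and 100 − 20.0 − 40.0 = 40.0%.

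**2. Can dual use differ with equal cessation?** Dual use = (1 − abstinence) × ENDS share among continuing smokers. With abstinence 30% in both arms (EEC v TAU, Wald 95% CI, n = 35 per arm):

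| ENDS share | Dual use | Difference | 95% CI |
|---|---|---|---|
| 70% v 70% | 49% v 49% | 0 | not needed |
| 80% v 70% | 56% v 49% | 7 points | −16 to 30 |
| 70% v 40% | 49% v 28% | 21 points | −1 to 43 |

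With abstinence anywhere from 40% to 10%, the last two differences become 6 to 9 and 18 to 27 points. In every row the abstinence difference, reported alongside, is zero, with a half-width of 1.96 × √(2 × 0.30 × 0.70/35) = 21 points at 30% abstinence.

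**3. Does an unstated window break the subtraction?** Suppose 11 of 35 are abstinent, 17 both and 7 cigarettes only. If dual use were counted over 30 days, k people who used both products but stopped smoking 8 to 30 days earlier would enter both rates. Subtraction would give 35 − 11 − (17 + k) = 7 − k. A cross tabulation of abstinence by dual use avoids this: the cells are k abstinent and dual, 11 − k abstinent and not dual, 17 smoking and dual, 7 smoking and not dual. The 7 is read directly, and k sits in a cell that would be empty if the windows matched. No document supports a particular k or a 30-day window at follow-up.

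**4. ENDS only v neither.** 14/7/14/0 and 14/7/0/14 both give 40% dual use and 40% abstinent. The two rates cannot tell them apart.

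**5. Missing counted as smoking.** Take 15 of 50 missing in each arm and responder dual use of 56% v 49%.

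- Missing counted as dual: (35 × 0.56 + 15)/50 = 69.2% v (35 × 0.49 + 15)/50 = 64.3%; difference 4.9 points.
- Missing counted as cigarettes only: 35 × 0.56/50 = 39.2% v 35 × 0.49/50 = 34.3%; difference 4.9 points.

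Each arm's rate moves by 15/50 = 30 points, but the contrast does not move. With unequal loss it moves by the gap in missing fractions: 10 v 15 missing gives (15 − 10)/50 = 10 points between the two conventions.

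**6. What the diaries add.** SAP 2.3b (Phase 1 Procedures) schedules diaries for the 7 days before 3 months, SAP 2.3c carries the Phase 1 measures into Phase 2, and the Protocol (Phase 2, Daily Surveys) runs them for 12 weeks. SAP Table 2 marks selected tobacco and ENDS items for the diary. Both products are therefore recorded over the same days near the end of follow-up. Completion will be partial: SAP 2.3c cites 59% in weeks 1 and 2 of another study.

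**The case for a change.** The best case for a change is that it costs little. SAP Table 2 lists last use of tobacco and of ENDS in the outcome survey, so a table of the four states by arm would need only wording. The SAP's closing statement promises product-use data in relation to smoking outcomes, and two separate rates do not deliver the ENDS split among abstainers. The cross-tabulation sentence is generic, and the diaries are an incomplete substitute.

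These points stand: the supplied text gives no dual-use window, the two rates do not split abstainers by ENDS use, and the missing-as-smoking rule does not fix ENDS status. They show a report that could say more. They do not show a planned analysis that gives a wrong answer.

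The proposed table also has costs. Entry used a 30-day ENDS window, and SAP 2.1 recognises intermittent ENDS use. Under a 7-day ENDS rule, a smoker who vapes every two weeks and has changed nothing could move from dual at entry to cigarettes only at follow-up. The tobacco item in Table 2 is not specific to cigarettes, and the content of the Protocol's shortened survey is not shown. Cells would be small: 5/35 has a Wilson 95% CI of 6% to 29%, and 7/35 of 10% to 36%.

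The mechanism by arm is plausible but unproven. Table 1 describes usual treatment's stance on ENDS more firmly than SAP 2.1 and 2.3c do. Those descriptions are for the authors to reconcile; this point does not depend on which one holds.

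**Conclusion.** No change to the plan is needed. Dual use merges cigarette-only smokers with quitters by definition, but reading it as cessation would mean ignoring the abstinence outcome named in the same sentence. Under the assumed shares the dual-use gap unrelated to cessation runs from 0 to 21 points at 30% abstinence (up to 27 at 10%), always beside an abstinence difference of zero. The pilot claims no power, reads its intervals cautiously, and has primary hypotheses (call completion, satisfaction and quit-plan experience, beliefs) that are unaffected.

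What remains is a definitional gap in a secondary outcome. An analyst would state the dual-use window and denominator when reporting, and could describe ENDS use among abstainers from data already planned. The missing-value convention leaves the arm contrast unchanged when loss is equal, and the SAP's responder-only, multiple-imputation and varied-relapse analyses sit beside it. This conclusion assumes that abstinence and dual use are reported together, as SAP 2.4d plans. The study measures attachment was not supplied and may already settle the window.
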